A FEASIBILITY STUDY TO EVALUATE THE CLINICAL SAFETY OF NUTRISEAL™ NASOENTERAL FEEDING TUBE PLACEMENT USING THE NUTRISEAL™ NUTRIPLACE™ SYSTEM IN PATIENTS

Protocol Number: NUTRI-001 Principal Investigator: [name] Sponsor: Nutriseal L.P. Version Number: 1.1 February, 4 2018

Summary of Changes from Previous Version:

#	Section	Previous wording (Ver. 1.0)	New wording (Ver. 1.1)	Rationale for
				revision
1.	1.1- Number of Subjects and Sites (Synopsis)	Fifty (50) subjects will be enrolled at a single center by at least five operators. Prior to participating in this trial each operator will place a Nutriseal nasoenteral feeding tubes in a run-in patient to provide training on the use of the NUTRIPLACE System.	Fifty (50) subjects will complete the Procedure Visit (NasoEnteral Tube placement procedure, section 1.3) at a single center by at least five operators. This number (50 subjects) does not include screen failures. Prior to participating in this trial each operator will place a Nutriseal	To clarify that the 50 enrolled subjects will complete the Procedure Visit
			nasoenteral feeding tubes in a run-in patient to provide training on the use of the NUTRIPLACE System.	
2.	1.1 Sample size consideratio ns (Synopsis)	There is no statistically based sample size for this study which is being conducted to obtain confirmatory evidence to support the safety of using the NUTRIPLACE System as an adjunct to current placement practices for nasoenteral feeding tubes. Fifty (50) patients will provide evidence that the NET tube guidance system does not present new or different safety issues as compared to the predicate (confirmatory study).	There is no statistically based sample size for this study which is being conducted to obtain confirmatory evidence to support the safety of using the NUTRIPLACE System as an adjunct to current placement practices for nasoenteral feeding tubes. Fifty (50) patients completing the Procedure Visit (NasoEnteral Tube placement procedure) will provide evidence that the NET tube guidance system does not present new or different safety issues as compared to the predicate (confirmatory study). If less than 45 patients will complete the Follow-up Visit (confirmation of tube tip anatomical location, section 1.3), an enrollment of another 5 patients will be considered.	To clarify sample size population
3.	1.1 Exclusion Criteria (Synopsis) 5.2 Exclusion Criteria (Study population)		Upper airway obstruction	Upper airway obstruction was added as an exclusion criteria - Such obstructions can prevent insertion of feeding tube

4.	1.1 Exclusion Criteria (Synopsis) 5.2	Gastrointestinal surgeries		Gastrointestinal surgeries was omitted as an exclusion criteria- Not required as
	Exclusion Criteria (Study population)			population may well have undergone Gastrointestinal surgery.
				Moreover, participation in the study of a subject who underwent a Gastrointestinal surgery should be per Investigator's discretion as there is other exclusion criteria: "Patients must not have a significant concomitant illness that would adversely affect their participation in the study".
5.	 1.1 Exclusion Criteria (Synopsis) 5.2 Exclusion Criteria (Study population) 	Failed tube placement in the last seven days		Failed tube placement in the last seven days was omitted as an exclusion criteria- Redundant as Chest X-Ray demonstrates if there is presence of any lung damage caused by a previously inserted feeding tube
6.	5.4 Screen Failure	Screen failures are defined as participants who consent to participate in the clinical trial but are not subsequently entered in the study. A minimal set of screen failure information is required to ensure transparent reporting of screen failure participants, to meet the Consolidated Standards of Reporting Trials (CONSORT)	Screen failures are defined as participants who consent to participate in the clinical trial but are not subsequently entered in the study and do not complete the Procedure Visit. A minimal set of screen failure information is required to ensure transparent reporting of screen failure participants, to meet the Consolidated Standards of	To clarify the definition of screen failures

		publishing requirements and to	Reporting Trials (CONSORT)	
		respond to queries from	publishing requirements and to	
		regulatory authorities. Minimal	respond to queries from	
		information includes	regulatory authorities. Minimal	
		demography, screen failure	information includes	
		details, eligibility criteria, and	demography, screen failure	
		any serious adverse event (SAF).	details, eligibility criteria, and	
			any serious adverse event (SAF).	
7	9 2 Sample	This feasibility trial will include	This feasibility trial will include	To clarify sample size
	Size	fifty (50) patients and five	fifty (50) patients completing the	population
	Determinati	operators. Each operator must	Procedure Visit (NasoEnteral	h - h
	on	complete training on one run-in	Tube placement) and five	
		subject prior to participating in	operators. Each operator must	
		this study.	complete training on one run-in	
		,	subject prior to participating in	
			this study. Patients or patients'	
			LAR who chose not to	
			participate after informed	
			consent but prior to procedure	
			and patients who because of	
			system malfunction or because	
			of undiscovered or unreported	
			physical reasons (e.g.	
			deteriorating health, anatomical	
			anomalies, mechanical	
			obstruction, etc.) cannot	
			complete the Procedure Visit	
			(NasoEnteral Tube placement)	
			will be considered Screen	
			Failures, not be considered in	
			the total patient count, but will	
			be reported in the ITT dataset as	
			defined below. If less than 45	
			patients will complete the	
			Follow-up Visit (confirmation of	
			tube tip anatomical location), an	
			enrollment of another 5 patients	
			will be considered.	

STATE	MENT OF COMPLIANCE	1
1	PROTOCOL SUMMARY	2
1.1	Synopsis	2
1.2	Schema	5
1.3	Schedule of Activities (SoA)	6
2	INTRODUCTION	7
2.1	Study Rationale	7
2.2	Background	7
2.3	Risk/Benefit Assessment	8
2.3	3.1 Known Potential Risks	8
2.3	3.2 Known Potential Benefits	8
2.3	3.3 Assessment of Potential Risks and Benefits	8
3	OBJECTIVES AND ENDPOINTS	9
4	STUDY DESIGN	9
4.1	Overall Design	9
4.2	End of Study Definition	9
5	STUDY POPULATION	10
5.1	Inclusion Criteria	10
5.2	Exclusion Criteria	10
5.3	Female patients who are pregnant or lactating	10
5.4	Screen Failures	10
5.5	Strategies for Recruitment and Retention	11
6	STUDY INTERVENTION	12
6.1	Study Intervention(s)	12
6.2	Preparation/Handling/Storage/Accountability	13
6.2	2.1 Acquisition and accountability	13
6.2	2.2 Product Storage and Stability	13
6.2	2.3 Preparation and use	14
6.3	Measures to Minimize Bias: Randomization and Blinding	14
6.4	Concomitant Therapy	14
7	STUDY INTERVENTION DISCONTINUATION AND PARTICIPANT	
DISCO	NTINUATION/WITHDRAWAL	14
7.1	Participant Discontinuation/Withdrawal from the Study	14
7.2	Lost to Follow-Up	14
8	STUDY ASSESSMENTS AND PROCEDURES	14
8.1	Efficacy Assessments	14
8.2	Adverse Events and Serious Adverse Events	15
8.2	2.1 Definition of Adverse Events (AE)	15
8.2	2.2 Definition of Serious Adverse Events (SAE)	15
8.2	2.3 Classification of an Adverse Event	15
8.2	2.4 Time Period and Frequency for Event Assessment and Follow-Up	17

1 PROTOCOL SUMMARY

1.1 SYNOPSIS

Study Title	A Feasibilty Study to Evaluate the Clinical Safety of Nutriseal™ Nasoenteral Feeding Tube Placement using the Nutriseal™ NUTRIPLACE System in Patients.	
PROTOCOL NUMBER	NUTRI-001	
DEVICE DESCRIPTION	The Nutriseal [™] NUTRIPLACE [™] System is designed to aid qualified operators in the placement of the Nutriseal [™] NasoEnteral Tube [™] of 10 Fr to 12 Fr into the stomach or small intestine of patients requiring enteral feeding. The NUTRIPLACE System is intended as an adjunct to current placement practices for assisting clinical practitioners who place feeding tubes in adult patients.	
	The Nutriseal [™] NasoEnteral Tube has been specifically designed for use with the NUTRIPLACE [™] System and is intended for placement in the stomach or small intestine. It is intended for use in adult patients who require intermittent or continuous feedings via the nasogastric or nasoenteric route.	
Study Objectives	The objective of this study is to assess the safety of the NUTRIPLACE System as an adjunct to current practices for placement of nasoenteral feeding tubes.	
Study Design	The study is a prospective, single center, non-randomized clinical trial in patients that require placement of a nasoenteral feeding tube as a result of their current medical condition.	
Number of Subjects and Sites	Fifty (50) subjects will complete the Procedure Visit (NasoEnteral Tube placement procedure, section 1.3) at a single center by at least five operators. This number (50 subjects) does not include screen failures. Prior to participating in this trial each operator will place a Nutriseal nasoenteral feeding tubes in a run-in patient to provide training on the use of the NUTRIPLACE System.	
DURATION OF PARTICIPATION/STUDY	Each patient's individual participation will last approximately 20-48 hours. It is expected the entire study will take approximately two (2) months to complete.	
STUDY ENDPOINTS	Primary Endpoint:	
	Procedure success: Nasoenteral tube (NET) can be placed in the correct anatomical position without occurrence of guidance-related adverse events.	
	Additional Assessments:	

	Procedure Metrics: Number of placement attempts required				
	Safety: Adverse Events				
Sample Size Considerations	There is no statistically based sample size for this study which is being conducted to obtain confirmatory evidence to support the safety of using the NUTRIPLACE System as an adjunct to current placement practices for nasoenteral feeding tubes. Fifty (50) patients completing the Procedure Visit (NasoEnteral Tube placement procedure) will provide evidence that the NET tube guidance system does not present new or different safety issues as compared to the predicate (confirmatory study). If less than 45 patients will complete the Follow-up Visit (confirmation of tube tip anatomical location, section 1.3), an enrollment of another 5 patients will be considered.				
SCHEDULED VISITS	This study is an acute safety assessment of the NUTRIPLACE System covering the guidance functionality of the System.				
	Screening The screening visit will occur at time zero and will assess eligibility for the study and obtain informed consent.				
	Procedure The study procedure may occur within two days of screening. Informed consent will affirmed and the patient will be considered enrolled.				
	Final Follow Up The final follow-up visit will occur 20-48 hours following the procedure.				
INCLUSION CRITERIA	 Patients must be ≥21 years of age Patients must require placement of a nasoenteral feeding tube Patients have an endotracheal tube, OR Do not have an endotracheal tube but are sedated and/or classified as obtunded¹ at the time of placement Patients or legal authorized representative must be able to understand and adhere to all protocol procedures and be willing and able to provide written informed consent² 				
Exclusion Criteria	 Patients must not have a history of: Esophageal varices or ulcers Upper airway obstruction Upper GI stenosis or obstruction 				

Obtundation level evaluation is based on Glasgow-Coma scale with a score of between 9 and 12. Sedation level is based on Richmond Agitation-Sedation Scale (RASS) score of -2 or less.
 ² Consent may be provided by patient's legal authorized representative.

	 Trauma involving sinuses, nares face or neck that would prevent NG tube insertion Deformities of the sinus cavities and/or skull base Esophageal cancer or neoplasm Patients must not have a significant concomitant illness that would adversely 			
	affect their participation in the study			
	Female patients who are pregnant or lactating			
STATISTICAL ANALYSIS	All data will be reported using summary statistics.			
OTHER CONSIDERATIONS	No core lab will be charted for this study; thus, judgements regarding placement will be based on the investigator's assessment of X-Ray images. Assessments of relatedness of any noted adverse events to the study device will be adjudicated by a Clinical Events Committee (CEC). No DSMB will be chartered for this study based on the well- understood safety profile.			
US REGULATORY STATUS	The NUTRIPLACE System is considered a non-significant risk investigational device in the United States.			

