2.2 BACKGROUND

Enteral nutrition is the preferred route for the provision of nutritional support in most critical ill patients with functional gastrointestinal tract. The nasoenteric tube (NET) are easily placed at the bedside. Patients that most commonly require a NET are in the surgical, intensive care, neonatal and pediatric settings^{1,2}. Enteral tube feeding is thought to preserve the integrity of the gut mucosa, and to reduce infectious complications. Achieving early enteral nutrition (EN) in critically ill patients is associated with fewer major complications, reduced mortality and length of hospital stay, and significant cost savings^{3,4,5,6,7}.

It is estimated that approximately 1.2 million feeding tubes are placed blindly each year in the United States alone^{2,8,9,10,11}. Despite the obvious advantages of the enteral tube feeding, inadvertent placement of NET into the airway is relatively common and can result in significant pulmonary injury including pneumothorax and pneumonia. Airway misplacement occurs in 1.2–4 % of blind NET insertions, with 0.2 to 1.2% of all the feeding tube placements cause pulmonary complications to patients^{3,12,13,14,15,9}.

The gold standard for detecting inadvertent placement of a feeding tube in the lungs is radiography. However, because of its cost, possible delay of feedings while waiting for radiography, and risk for radiation exposure, clinicians continue to seek for alternative methods to confirm correct placement^{3,16}.

All the above mentioned, emphasizes the fact that safe and effective delivery of nasoenteral tube feedings requires assurance that the feeding tube tip is in a proper position¹⁷.

The NUTRIPLACE System is an electromagnetic tracking system which tracks the path of the feeding tube during placement. The System utilizes an ElectroMagnetic (EM) sensor in the NET's distal tip and a field generator as well as plate sensor (patient angle) and reference sensor (provides horizontal scaling of the body contour of the patient) and a Stylus which marks two anatomical landmarks (Xiphoid Process and Suprasternal Notch).

The benefit of the system when NET is misdirected into the pulmonary system is a real-time visual tracing, which may prompt users to withdraw the tube and reinsert it.

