6.3 MEASURES TO MINIMIZE BIAS: RANDOMIZATION AND BLINDING

This is an open label, non-randomized feasibility trial with limited bias expected. Bias in this study will be controlled through use of an independent CEC that will review and assess relatedness of reported adverse events to the NUTRIPLACE System.

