8.2.3.3 EXPECTEDNESS

The investigator will be responsible for determining whether an adverse event (AE) is expected or unexpected. An AE will be considered unexpected if the nature, severity, or frequency of the event is not consistent with the risk information previously described for the study intervention in the IB or the instructions for use.

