9 STATISTICAL CONSIDERATIONS

9.1 STATISTICAL HYPOTHESES

There is no formal statistical hypothesis for the primary endpoint of this feasibility trial. The primary endpoint is defined as procedure success, e.g., NET tube can be placed in the correct anatomical position without occurrence of guidance-related adverse events.

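### The Synopsis promises confirmatory evidence of no safety difference from the predicate, which a single-group descriptive study of 50 patients cannot give

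*Combined protocol and SAP*

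**What the plan says.** The Sample Size Considerations row of section 1.1 first states that 50 has no statistical basis. It then describes the study as "being conducted to obtain confirmatory evidence to support the safety of using the NUTRIPLACE System as an adjunct to current placement practices", and says that 50 patients who complete the Procedure Visit "will provide evidence that the NET tube guidance system does not present new or different safety issues as compared to the predicate (confirmatory study"). This is current text, not only an entry in the summary of changes.

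The rest of the protocol describes something more modest:

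- The Statistical Analysis row of section 1.1: "All data will be reported using summary statistics".
- Section 6.3: "This is an open label, non-randomized feasibility trial with limited bias expected".
- Section 9.1: "There is no formal statistical hypothesis for the primary endpoint of this feasibility trial".
- Section 9.4 calculates procedure success in each dataset and adds descriptive statistics. It plans no interval estimate.

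In the supplied current text the predicate is mentioned only in the Synopsis sentence. It is not identified, and no rate or event profile is given for it.

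**The concern.** The Synopsis sentence announces a comparative conclusion in advance and labels it confirmatory. Such a conclusion needs either a comparator group or a prespecified external reference, with a margin or performance goal. The plan has neither.

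The objective of the study is safety, so this is the sentence a reader would rely on when the results appear. As worded, few or no guidance-related adverse events could be reported as prespecified confirmatory evidence that safety does not differ from the predicate. Because only point summaries are planned, a bare 0% or 100% would not show how much uncertainty remains.

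**Working it through.** **The plan's own figure.** There is no calculation to reproduce. Section 1.1 says that 50 is not statistically based, and the documents give no alpha, power, effect size, predicate rate or margin. The check is therefore what 50 patients can show.

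**Inputs**

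- n = 50 completing the Procedure Visit (sections 1.1 and 9.2).
- n = 45, the follow-up count below which five more patients are considered (same sections).
- n = 55, which is 50 plus those five, or 50 plus five run-in patients.
- The only event rates in the documents are in section 2.2: "Airway misplacement occurs in 1.2–4 % of blind NET insertions", "with 0.2 to 1.2% of all the feeding tube placements cause pulmonary complications to patients". They concern blind insertion and feeding tube placements in general. I use them, and the doubled values 2.4% and 8%, as illustrative assumptions. They are not predicate rates or guidance-related adverse event rates.

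**Step 1: upper limit after zero events.** The exact two-sided 95% upper limit for 0/n is 1 − 0.025^(1/n).

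- n = 45: 1 − 0.025^(1/45) = 0.0787, or 7.9%
- n = 50: 1 − 0.025^(1/50) = 0.0711, or 7.1%
- n = 55: 1 − 0.025^(1/55) = 0.0649, or 6.5%

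All three exceed the top of both background ranges (4% and 1.2%).

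**Step 2: chance of a clean result.** P(0 events in 50) = (1 − p)^50.

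| Assumed true rate p | P(0/50) | P(at least one) |
|---|---|---|
| 0.2% | 0.905 | 0.095 |
| 1.2% | 0.547 | 0.453 |
| 2.4% | 0.297 | 0.703 |
| 4% | 0.130 | 0.870 |
| 8% | 0.015 | 0.985 |

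At 1.2%, no event is the more likely outcome. If the rate were twice that, no event would still be seen about 30% of the time. A frequent problem (8%) would almost certainly show itself.

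**Step 3: procedure success.** Clopper-Pearson 95% limits: 50/50 has a lower limit of 0.025^(1/50) = 92.9%; 48/50 has an interval of 86.3% to 99.5%.

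**Step 4: size of a study that could address rates.** With zero events, the two-sided 95% upper limit falls below a reference rate p once n reaches ln(0.025)/ln(1 − p), rounded up. That is 91 for 4%, 306 for 1.2% and 1,843 for 0.2%. A two-arm comparison to detect a doubling (two-sided 0.05, 80% power) would need about 553 per arm for 4% against 8%, or 1,926 per arm for 1.2% against 2.4%. With 50 per arm the power would be about 13% and 7%.

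**Step 5: the qualitative reading.** The sentence may refer to kinds of event rather than rates. A comparison of kinds needs a predicate list and a step that applies it. Section 8.2.3.3 calls an event unexpected when it is "not consistent with the risk information previously described for the study intervention in the IB or the instructions for use", so the reference is the study device. Section 10.1.5 has the Clinical Events Committee adjudicate the involvement of the subject device. Neither step refers to the predicate.

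**The case against.** The strongest reply is that new or different issues most naturally means kinds of event, and that the protocol has a route for finding these. Section 2.3.1 lists risks of nasoenteral tubes in general. Section 8.2.2 defines an unanticipated device effect as a serious effect not already identified in the protocol, Investigator's Brochure or Instructions for Use. Section 8.2.3.2 classifies relatedness to the guidance function. The attachments were not supplied and may describe the predicate. This stands in part: such a review could flag a serious event of a new kind. It does not supply the missing comparison, because the lists named are general or belong to the study device, the unanticipated-effect route covers only serious events, and section 9 plans no use of predicate information from any source.

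A second reply is that the limits are disclosed: no statistical basis for 50, no hypothesis, a feasibility label throughout, and a claim only to provide evidence. The disclosure is real and keeps this from being a fault in the sample size. But it explains how 50 was chosen; the next sentence still says what 50 will show.

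A third reply is that the illustrative rates are not the predicate's and that patients treated by about five operators may not be independent. Both points are fair. The upper limit of 7.1% needs no assumed rate, but it does assume independence, and positive correlation within operators would generally make the uncertainty larger.

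**Conclusion.** The concern holds. Section 1.1 claims a comparative, confirmatory property that the supplied design and analysis lack. After 0/50, true rates up to about 7% remain compatible with the data, assuming independent patients and exact two-sided 95% limits. The probabilities of a clean result also rest on the section 2.2 rates and their doubles, used as illustrations because no predicate rate is given.

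The fault lies in the stated inference. A descriptive feasibility study of 50 patients is reasonable, and it could reveal a frequent problem; it cannot exclude a rare one or show that safety matches the predicate. Study conduct is unaffected, but the wording should be corrected because it governs what may be concluded.

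**What to change.** **Section 1.1, Sample Size Considerations.** Delete both uses of the confirmatory label and the claim about the predicate. Replace with:

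> The 50 patients who complete the Procedure Visit give a descriptive estimate of procedure success and of the guidance-related adverse event rate. No comparison with the predicate can be concluded. For example, 0 guidance-related adverse events in 50 patients would give an exact two-sided 95% upper limit of 7.1% (7.9% at n = 45, 6.5% at n = 55).

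**Section 9.4.** Add:

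> Procedure success and the proportion of patients with at least one guidance-related adverse event will be reported with exact (Clopper-Pearson) 95% confidence intervals, using the actual denominator of each dataset in section 9.3.

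The actual denominators matter. Section 9.2 reports screen failures in the ITT dataset, and the Full Cohort adds the run-in patients, so neither need equal 50.

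**Cost.** Wording in two sections and one line of analysis code per dataset. The stated claim becomes less favourable. No patients, visits or data items are added.

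If the sponsor wants to keep the comparison, it must prespecify the predicate data, a margin or performance goal, and a matching sample size. The figures in Step 4 suggest that this would be a much larger study.
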